Protocol Title: NAPS: Niacin for Parkinson's Disease

Principal Investigator: [name]

1. Objectives

Describe the purpose, specific aims, and hypothesis:

(1) examine the blood, urine and spinal fluid of persons with Parkinson's to look for evidence of inflammation and; (2) whether 18 months of vitamin B3(niacin or niacinamide) supplementation may reduce the inflammation and/or improve symptoms.

Blood samples will be analyzed through Enzyme Linked Immuno Sorbent Assay (ELISA). We will examine GPR109A levels in WBCs, NAD/NADH ratio in RBCs, inflammatory and non-inflammatory cytokines (Serum and CSF levels of following twenty-seven cytokines EGF, FGF2, Eotaxin, TGFa, GCSF, Flt3L, GMCSF, IFNg, IL10, MCP3, IL12P40, IL12P70, IL13, IL15, sCD40L, IL1RA, IL1a, IL1b, IL5, IL6, IL7, IL8, MIP1a, MIP1b, TNFa, TNFb and IP10), and niacin metabolites in plasma and urine. Blood samples will be analyzed through FACs, Seahorse, and protein (total and phosphorylated) analysis to understand biomarkers of PD and effects of niacin in PD.

2. Background

Describe the background and rationale for the study:

Inflammation plays a central role in Parkinson's disease (PD) pathology [1] as evidenced by the presence of microglia in the substantia nigra in post-mortem samples [2] as well as activated microglia and cytokines in clinical and animal studies [3]. The use of non-aspirin non-steroidal anti-inflammatory drugs was found to reduce the risk of PD [4]. We recently identified an anti-inflammatory receptor GPR109A that is upregulated in PD [5]. Niacin has a high affinity for this receptor, suggesting that it (niacin) may play an important role in reducing inflammation in PD. We also found that individuals with PD have a chronic niacin deficiency [5]. Using seed funding from the local PD chapter, we obtained pilot data which suggested that restoring the deficiency via over-the-counter (OTC) supplementation reduced inflammation and decreased the severity of the disease symptoms [6]. In this VA-funded study, we will determine the effect of 18 months OTC niacin or niacinamide supplementation on inflammation (as assessed in the blood and spinal fluid) and severity of the PD symptoms.

References

1. Barnum CJ, Tansey MG (2010) Modeling neuroinflammatory pathogenesis of Parkinson's disease. *Prog Brain Res* 184: 113–132.

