Blood (2-3 tsp), urine and spinal fluid samples, over-the-counter (non-prescription) vitamin B3 (Niacin or Niacinamide) supplementation.

Blood Collection

Ten ml blood samples will be collected by venipuncture following standard procedures and processed within 4 hours as described earlier ([name] et al., 2014 doi.org/10.1371/journal.pone.0109818). Briefly, purple-top ethylenediaminetetraacetic acid (EDTA) tubes will be used to collect the blood sample and immediately kept in ice. Whole blood will be spun and leukocytes (WBCs) will then be collected and placed in fresh tubes, re-suspended in 4 ml of ACK Lysing Buffer (Lonza cat # 10-548E) and be incubated for 10 min at room temperature before being spun again at 300 ×g for 5 min. The process will be repeated one more time. Supernatant will be discarded from the clean WBCs pellet. WBCs pellets will be washed twice with 1 ml of PBS and WBCs pellets will then be stored at -80 °C until further analyses ([name] et al., 2014).

Analytical flow cytometry

As described previously (Stranahan et al., 2016), whole blood cells will be incubated with antibodies for surface markers including CD11b, CD68, F4/80 (M1), CD206 (M2), and GPR109a. Next, cells will be fixed and permeabilized using fix/perm concentrate (eBioScience) before incubation with antibodies for intracellular staining of IL-10 (functional M2 s). Cells will then be washed and run through a four-color flow cytometer (FACS Calibur). Data will be collected using Cell Quest software. Samples will be double-stained with control IgG (isotypes) and cell markers to assess any spillover signal of fluorochromes. Gating will exclude dead cells and debris using forward and side scatter plots.

Western Blot

WBCs will be separated as described previously ([name] et. al 2014). WBCs will be subjected to lysis by RIPA buffer with a protease inhibitor cocktail and protein concentration will be measured by Bradford reagent (Bio-Rad). Again the samples will be subjected to western blot using Bio-Rad 4–15% SDS-PAGE then transferred to PVDF membrane followed by incubation with respective antibody overnight and developed with an ECL kit (Giri et al., 2007).

Saehorse

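### Phosphorylated protein is a planned read-out, but the stated Western blot lysis buffer names protease inhibitors only, so phospho results will be noisier and any group difference attenuated

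*Combined protocol and SAP*

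**What the plan says.** Section 1 (Objectives) lists flow cytometry, "Seahorse, and protein (total and phosphorylated) analysis to understand biomarkers of PD and effects of niacin in PD". Phosphorylation is therefore a named read-out, tied to the treatment question.

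Section 6a (Western Blot) states that "WBCs will be subjected to lysis by RIPA buffer with a protease inhibitor cocktail and protein concentration will be measured by Bradford reagent". After gel separation and transfer to a membrane, the method is "followed by incubation with respective antibody overnight and developed with an ECL kit". The antibody targets are not listed.

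Section 6a (Blood Collection) covers the steps before lysis. "Ten ml blood samples will be collected by venipuncture following standard procedures and processed within 4 hours as described earlier" sets the delay, and the EDTA "tubes will be used to collect the blood sample and immediately kept in ice". The white cells are resuspended in red-cell lysing buffer, to "be incubated for 10 min at room temperature before being spun again". That step is done a second time, followed by two PBS washes and storage at -80 °C.

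Sections 4 and 8a add that recruitment is closed and that what remains is analysis of samples already in hand.

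**The concern.** The Western blot paragraph names its protective additive, and that additive protects against protein breakdown only. Breaking cells open also releases phosphatases, which remove phosphate groups and which protease inhibitors do not stop. This is general biochemistry; the document does not state it. Total protein is protected by the recipe as written, but its phosphorylated fraction is not.

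At stake is one laboratory objective. If phosphate is lost to a varying degree from sample to sample, the phospho signal carries extra variation unrelated to treatment, and a real niacin or niacinamide effect becomes harder to see. A null phospho result would then be hard to interpret, because it could mean no effect or a degraded measurement.

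**Working it through.** No arithmetic in the plan bears on this point. The check compares the planned read-out with each handling step.

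**1. Which assay carries the phospho read-out?** One sentence of section 1 names three kinds of analysis: FACS, Seahorse, and total and phosphorylated protein. Section 6a has three method paragraphs: flow cytometry, Western blot and Seahorse. The flow panel is CD11b, CD68, F4/80, CD206, GPR109a and IL-10, with no phospho-target. Seahorse measures oxygen consumption. That leaves the Western blot.

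**2. Where might phosphorylation be preserved?**

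| Step (section 6a) | Condition | Phosphatase inhibitor named? |
|---|---|---|
| Draw to processing | On ice, up to 4 hours | No |
| Red-cell lysis | Room temperature, 2 × 10 min = 20 min | No |
| Washes | PBS, twice | No |
| Storage | -80 °C | No |
| White-cell lysis | RIPA plus protease inhibitors; temperature and duration not given | No |

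Ice and freezing slow enzyme activity. The two room-temperature incubations and the lysis step have no stated safeguard for phosphate groups.

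**3. Bias or noise?** Section 6b describes a placebo-controlled design with visits at baseline, 6, 12 and 18 months. Section 7a analyses outcomes with a mixed model using group and time. Section 6a gives one handling procedure for everybody. A handling shift shared by all arms at a visit is therefore largely removed from the between-group comparison. What remains is loss that varies from sample to sample.

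**4. Can the size be derived?** Let s be the standard deviation of the read-out without phosphate loss, x the added standard deviation from variable loss (independent of s), and f the average fraction of signal that survives. The standard error of a comparison grows by a factor of √(1 + x²/s²), and a difference in raw signal shrinks to f times its true size. The document gives none of s, x and f. The power tables in section 7b cover UPDRS motor, sleep measures and the GPR109A correlation, and have no row for phosphorylated protein. The direction is clear, but the size cannot be obtained.

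**5. Is there still something to change?** Pellets are frozen before lysis, so the lysis buffer can still be changed for any pellet not yet lysed. The earlier steps are finished for samples already collected.

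**The case against.** **The link to the Western blot is inferred.** The paragraph names no phospho-target. Section 1 also mentions ELISA, which has no paragraph in section 6a, so 6a is not a complete list of methods. This stands as a caution. Even so, section 1 names ELISA apart from the protein analysis, and no other described method fits.

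**The text is a summary.** It describes blood processing in brief and cites earlier papers from 2014 and 2007, so an inhibitor may be used in practice. That is possible and cannot be settled here. But the plan spells out its buffer and names one class of inhibitor, and a laboratory following it would leave phosphatases unblocked. If an inhibitor is already used, one added phrase closes the point.

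**Blood is kept on ice.** True, and this reduces loss before processing. It does not cover the room-temperature incubations or the lysis.

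**Stronger readings the document does not support.** A reader might infer that handling differences between visits would pass for a niacin effect. The placebo arm and the group-by-time analysis largely remove a visit-wide shift; only handling that differed by arm would bias the comparison, and none is described. A reader might also want a figure for lost power. Any such figure would rest wholly on assumed variation, since no power is planned for this read-out. Nor does the plan define a phospho-to-total ratio as an endpoint, so no such endpoint can be said to be compromised.

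**Conclusion.** The point holds as a minor but concrete weakness of the laboratory method. As written, the only described assay that fits the phosphorylated-protein objective leaves phosphatases unblocked at lysis. The expected consequence is added noise and attenuation of any phospho-protein difference between groups; its size is unknown.

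Three assumptions underlie this: that the Western blot is the phospho assay (a strong inference), that the stated recipe is the one used, and that unblocked phosphatases act during lysis (general biochemistry). Directional bias would require delay, storage or batch to differ by arm. The primary outcome (UPDRS III) and the sample size are unaffected.

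**What to change.** In the Western Blot paragraph of section 6a:

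- Specify ice-cold RIPA with both protease and phosphatase inhibitor cocktails for every stored pellet not yet lysed.
- Run phosphorylated and total protein on the same lysate.
- Do not pool these results with lysates made without the phosphatase inhibitor.
- Report all phospho results as exploratory. Loss before freezing cannot be undone by a better lysis buffer. Where draw-to-freeze time was recorded, use it when interpreting the results.

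Adding inhibitor to the PBS washes would probably help no one now, because only collected samples remain to be analysed.

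The cost is one inexpensive reagent and a few lines of text. The downside is that earlier lysates cannot be combined with new ones, so fewer samples may contribute to each phospho analysis.

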Subjects will be excluded if they had previous brain surgery or other severe neurological problems – intracerebral hemorrhage, traumatic brain injury, central nervous system malignancy, active CNS infection, significant stroke, Alzheimer disease or any type of implanted stimulator including but not limited to Deep Brain Stimulator (DBS) or pacemaker. All subjects must be without evidence of dementia, defined as a score > 24 the Mini-Mental State Examination and able to understand test instructions. Subjects must not have functional blindness (inability to participate in gait and visuomotor assessments) or lower limb amputation higher than the forefoot or any orthopedic problem that precludes performance of physical tests. Subjects must not have known allergy to vitamin B3.

Significant cardiac, pulmonary, hepatic, gastrointestinal, or renal disease (e.g., New York Heart Association Class III or IV congestive heart failure; endocarditis; pulmonary insufficiency symptomatic at rest or with mild physical exertion; acute or chronic hepatitis; renal failure requiring dialysis; second and third degree AV block or sick sinus syndrome), or uncontrolled/advanced diabetes are also exclusionary factors.

Subjects will be excluded if they are taking B3 but will be included if they are taking B complex that has very low dose B3 (25 mg) which has minimal effects on GPR109A (based on our unpublished observation).

Overall, [name] will exercise his clinical judgment to exclude a subject from the study if, in his opinion, he feels that a patient presents with a set of comorbidities which renders them unsuitable for the study.

4. Number of Subjects/Records/Samples Collected

Indicate the total number of subjects to be accrued/records reviewed/samples collected across all sites:
100 No new recruitment.

5. Recruitment Methods

Describe when, where, and how potential subjects will be recruited:

VA clinic (including medical records), word of mouth.

6. Procedures Involved

a. *Describe the procedures involved to include those procedures that are standard evaluation and/or care and those that are solely for research purposes:*

Standard procedures: basic physical examination for strength, speed, coordination, tremor, flexibility, rigidity and reaction time

Research procedures: questionnaire and tests to document health and cognitive status,

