Oxygen consumption rate (OCR) is measured before and after the addition of inhibitors to derive several parameters of mitochondrial respiration. Initially, baseline cellular OCR is measured, from which basal respiration can be derived by subtracting non-mitochondrial respiration. We will study OCR before and after niacin treatment in PD.

b. Describe and explain the study design:

Baseline, 6 month, 12 month and 18 months repeated measures placebo-controlled study

Group 1 – Niacin Arm: 30 PD subjects	Group 2 – Niacinamide Arm: 30 PD subjects	Group 3 – Placebo Wait-listed Arm: 30 PD subjects
Oral 100 mg fixed dose twice daily x 18-months (200 mg total / day) with assessments @ baseline, 6 month, 12 month and 18 months	Oral 100 mg fixed dose twice daily (200 mg total / day) x 18-months with assessments @ baseline, 6 month, 12 month and 18 months	Oral placebo twice daily x 18-months with assessments @ baseline, 6 month, 12 month and 18 months

c. Describe the procedures performed to lessen the probability or magnitude of risks:

Use of slow-release supplement to minimize potential skin itching

d. Describe the duration of an individual subject's participation in the study and the time involved:

18 months supplement study with a baseline, 6 month, 12 month and 18 months each lasting about 1 to 1.5 hr.

7. Data and Specimen Management

a. Describe the data analysis plan, including any statistical procedures:

We will use the Unified Parkinson's Disease Rating Scale (UPDRS) III (Motor Section) as the primary pre- and post-treatment outcome assessment that is recommended for PD studies. Significant changes in outcome measures will be determined by performing a Mixed model analysis of variance, with Groups as the independent factor and Time as the repeated factor.

N/A

b. When applicable, provide a power analysis:

Based on the preliminary data using unpaired simple effects analyses, the minimum number of subjects needed per group to detect a statistical significance @ $p = .05$, 2-tailed and 80% power of detection are as follows:

Outcome measures	Effect size (based on Cohen's d)	# Subjects/group
UPDRS motor	1.46	14
Sleep efficiency (pilot data)	0.97	8

The sample sizes are based on a large effect size, i.e., a grossly observable and clinically meaningful treatment effect. We have demonstrated that this is a reasonable expectation based on the actual effect sizes of the human preliminary data that we have shown. We used simple effects analyses as

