Version Date: 1/4/2019, 7/19/2021,

2/9/2022, 10/26/2022

the basis for the sample size calculations because any sample size calculations based on the full design would require knowledge of the intra-class correlation across the treatments, as well as the carry-over, group, and period effects.

Correlation statistics. Based on the preliminary data's correlation coefficients (r) obtained via simple linear independent correlation tests comparing the variables versus disease severity (UPDRS motor section), the minimum number of subjects needed per group to detect a statistical significance @ $p = .05$, and 80% are as follows:

Outcome measures	r	# Subjects/group
GPR109A levels	0.59	20
Total Sleep Time	-0.57	18
Time to Fall Asleep	0.79	8
Sleep Efficiency	-0.73	10

Based on the simple effects and correlation power analyses above, we propose to collect 30 PD subjects per group (total 90) to account for potential subject dropouts, experimental/data corruption and/or an unexpected increase in the variability of the data. We plan to recruit about 100 subjects to take into account potential drop-outs and an unexpected increase in the variability of the data which impacts the estimated statistical power.

c. *Describe how data and specimens will be handled:*

N/A

i. *What information will be included in that data or associated with the specimens?*

Please refer to 6a above. All data will be coded.

ii. *Where and how data and/or specimens will be stored?*

Specimens: Core lab. Data: Secured computer. ICD will be stored in a locked cabinet. NOTE: All data including specimens will be coded. Specimens will be stored at the VA in room 6B-127, and data will be stored in room 6B-128 (PI's Office).

iii. *How long will the data and/or specimens be stored?*

Indefinitely

iv. *Who will have access to the data or specimens?*

Research team

v. *Who is responsible for receipt or transmission of the data and/or specimens?*

[name] (PI)

vi. *How will data and/or specimens be transported?*

Manually

8. Provisions to Monitor the Data to Ensure the Safety of Subjects

This study involves no more than minimal risk study and this section is not required. **N/A**

The plan might include establishing a data monitoring committee and a plan for reporting data monitoring committee findings to the IRB and the sponsor.

a. *Describe the plan to periodically evaluate the data collected regarding both harms and benefits to determine whether subjects remain safe.*

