Subjects will be contacted the day after their study test participation to make sure that they did not experience unexpected or severe reactions to the vitamin supplement and optional lumbar puncture. A log will be kept to document the contact and relevant information from the subject. Subjects will also be given a 24-hour hotline to report any adverse event that they think is related to the study.

The CSR&D DMC will review the study data every six months for adverse event occurrence, safety monitoring, overall performance and data generation. Any recommendations will be submitted to the IRB.

Study is completed with recruitment. This is only the analysis of collected samples. No identifiers are used in analysis.

b. *Describe what data are reviewed, including safety data, untoward events, and efficacy data.*

Safety and untoward events related to the vitamin supplement and optional lumbar puncture will be reviewed. NA

c. *Describe how the safety information will be collected (e.g., with case report forms, at study visits, by telephone calls with participants).*

Safety information will be collected by telephone calls or emails with the participants. NA

d. *Describe the frequency of data collection, including when safety data collection starts.*

Data will be collected by the researchers at baseline, 6 month, 12 month and 18 months of the study. Subjects will be instructed to contact the researchers as soon as possible if they experience any adverse events that they think is related to the study.
NA

e. *Describe who will review the data.*

[name] will be the main person to review the data. He will consult with [name] if needed. The DSMB will also review the data every 6 months.

f. *Describe the frequency or periodicity of review of cumulative data.*

Cumulative data will be reviewed by the lab every month to ensure adherence to the approved protocol. Every 6 months it will be reviewed by DSMB.

g. *Describe any conditions that trigger an immediate suspension of the research.*

If a subject reports an unexpected adverse event, the study will be suspended. The study will resume if it is determined that the event is unrelated to the study.

9. Withdrawal of Subjects

N/A

a. *If applicable, describe anticipated circumstances under which subjects will be withdrawn from the research without their consent.*

Click here to enter text.

N/A

b. *If applicable, describe any procedures for orderly termination.*

Click here to enter text.

N/A

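### The sample-size tables in section 7b cannot be reproduced: the larger effect (d = 1.46) is given 14 per group and the smaller (d = 0.97) only 8, where 9 and 18 are needed

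*Combined protocol and SAP*

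**What the plan says.** Section 7b of the combined protocol and SAP gives minimum group sizes from unpaired simple-effects analyses of preliminary data, at p = .05, "2-tailed and 80% power of detection are as follows". Two rows follow:

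| Outcome | Cohen's d | Printed n per group |
|---|---|---|
| UPDRS motor (primary outcome, section 7a) | 1.46 | 14 |
| Sleep efficiency | 0.97 | 8 |

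The second row is labelled "Sleep efficiency (pilot data").

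A second table, for correlations with UPDRS motor, gives "the minimum number of subjects needed per group to detect a statistical significance @ $p = .05$, and 80% are as follows". It names no tail:

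| Variable | r | Printed n per group |
|---|---|---|
| GPR109A levels | 0.59 | 20 |
| Total sleep time | -0.57 | 18 |
| Time to fall asleep | 0.79 | 8 |
| Sleep efficiency | -0.73 | 10 |

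The section then concludes: "Based on the simple effects and correlation power analyses above, we propose to collect 30 PD subjects per group (total 90"), with the margin there "to account for potential subject dropouts, experimental/data corruption and/or an unexpected increase in the variability of the data". It gives no dropout rate. On status, section 4 has "100 No new recruitment" and section 8a has "Study is completed with recruitment. This is only the analysis of collected samples".

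**The concern.** With the test, alpha and power held fixed, the required sample size falls as the effect grows. The first table goes the other way, so at least one of its four numbers, or the stated basis, is wrong. The same ordering fault separates the first two rows of the correlation table.

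These tables are the only quantitative support offered for 30 per group, and one row is the primary outcome. If the figures went into a report unchanged, a reader could not reproduce them. A reader also could not tell whether the primary-outcome row is generous or short.

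**Working it through.** **Inputs (section 7b).** Unpaired two-group comparison, alpha 0.05 two-tailed, power 80%; d = 1.46 and 0.97; printed n = 14 and 8 per group; planned n = 30 per group.

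**1. Trying to reproduce the printed sizes.** The normal approximation is n per group = 2(z₀.₉₇₅ + z₀.₈₀)²/d², with (1.960 + 0.842)² ≈ 7.85.

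- d = 1.46: 2 × 7.85 / 2.132 = 7.4, so 8.
- d = 0.97: 2 × 7.85 / 0.941 = 16.7, so 17.

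The two-sample t-test (noncentral t, noncentrality d√(n/2), 2n − 2 degrees of freedom) gives 8.44, so **9**, and 17.70, so **18**. The printed 14 and 8 are not reproduced.

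**2. Power at the printed sizes (noncentral t, two-tailed).**

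- d = 1.46, n = 14: noncentrality 1.46 × √7 = 3.86, power 96.1%.
- d = 0.97, n = 8: noncentrality 0.97 × √4 = 1.94, power 43.9%.

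Read the other way, 14 and 8 per group detect d of about 1.10 and 1.51 with 80% power.

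**3. Are the two sizes simply exchanged?**

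| Pairing | Two-tailed power | One-tailed power | One-tailed n needed |
|---|---|---|---|
| d = 1.46, n = 8 | 77.5% | 87.1% | 6.60, so 7 |
| d = 0.97, n = 14 | 69.5% | 80.3% | 13.87, so 14 |

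An exchange alone fails under the stated two-tailed test. An exchange combined with a one-tailed test comes close (7 and 14 against 8 and 14) but contradicts the stated basis. Other variants also failed to give both printed rows: a paired test, 90% or 95% power, rank-test inflation, n read as a total over both groups, and a Bonferroni alpha.

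**4. Correlation table.** Fisher z: n = ((z_α + z₀.₈₀)/atanh|r|)² + 3. For r = 0.59 two-tailed, atanh = 0.678, so 7.85/0.459 + 3 = 20.1. The exact columns use the bivariate-normal distribution of r.

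| Absolute r | Printed n | Exact n, two-tailed | Fisher z, two-tailed | Exact n, one-tailed | Fisher z, one-tailed | Power at printed n, two-tailed / one-tailed |
|---|---|---|---|---|---|---|
| 0.59 | 20 | 20 | 20.1 | 16 | 16.5 | 82% / 89% |
| 0.57 | 18 | 21 | 21.7 | 17 | 17.7 | 73% / 83% |
| 0.79 | 8 | 9 | 9.8 | 8 | 8.4 | 73% / 84% |
| 0.73 | 10 | 12 | 12.1 | 10 | 10.2 | 74% / 84% |

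The first row fits a two-tailed test. The other three fit a one-tailed test: 8 and 10 match the exact method, and 18 matches Fisher z and is one above the exact 17. No single tail gives all four rows. Whatever the tail, 0.57 cannot need fewer subjects than 0.59.

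**5. Does 30 per group cover the printed effects?** Two-tailed power at n = 30 is above 99.9% (d = 1.46) and 95.9% (d = 0.97); the lowest correlation row has 92.8%. The largest recomputed minimum is 18 for the mean comparisons and 22 for the correlations (Fisher z, 21.7 rounded up). A group of 30 could therefore lose 30 − 18 = 12 subjects (40%) or 30 − 22 = 8 (27%), respectively, before falling below them.

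**The case against.** The strongest reply is that nothing depends on the faulty entries. The 30 per group rests on both tables plus a margin, and neither row of the first table is the largest printed minimum. That is 20, for GPR109A, and it does reproduce two-tailed. Full correction moves the largest minimum only from 20 to 21 (exact) or 22 (Fisher z). The printed 14 for the primary outcome also exceeds the 9 needed for d = 1.46, so that row looks conservative.

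Most of this stands, and it is why the point is minor. It does not rescue the tables: the other five of the six printed sizes do not reproduce under a two-tailed test. The primary-outcome row is conservative only if d = 1.46 belongs to UPDRS motor. If the two d values were exchanged, 14 per group gives 70% power, and the documents do not settle which is the case.

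Two further cautions are fair. First, the correlation table states no tail, so its two-tailed minimums rest on carrying over the basis of the first table. Fisher z rounded to the nearest whole number gives 16, 18, 8 and 10 one-tailed, which matches three rows by one method, but then the 20 for r = 0.59 is out of line. The ordering fault between 0.57 and 0.59 needs no assumption about tails. Second, an exchange plus a one-tailed test is only a possible origin, and the documents cannot confirm it.

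**Conclusion.** The concern holds, as a minor error in the stated figures. Under the section's own rule, the first table should read 9 and 18 per group if each d belongs to its printed row, against 14 and 8. The correlation table is out of order in its first two rows and mixes results that fit different tails.

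The finding that 30 per group is enough depends on two conditions: that the printed d and r values are the true pilot values, in whichever rows, and that each comparison is a single unadjusted test at .05. With a Bonferroni adjustment over the three pairwise group comparisons, power at 30 per group is still 99.9% (d = 1.46) and 89.8% (d = 0.97). If a printed effect size is itself a misprint, coverage for that outcome is unknown. Recruitment is closed, so the correction concerns the record, not enrolment or analysis.

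**What to change.** Check each effect size and its sample size against the pilot data, then restate section 7b before the figures are reported:

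- **First table:** give n under the stated two-tailed unpaired t-test, which is 9 (d = 1.46) and 18 (d = 0.97) if the d values are in the right rows.
- **Correlation table:** state the tail. Two-tailed is the consistent choice with the first table. Compute all four rows by one named method: exact 20, 21, 9 and 12, or Fisher z rounded up 21, 22, 10 and 13.
- **Optional:** add what the design can detect. With 30 evaluable subjects per group, an unpaired two-tailed .05 comparison has 80% power for d of about 0.74. The detectable d rises with dropout, for example to about 0.83 with 24 evaluable per group (an assumed loss of 6, since no dropout rate is given).

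The cost is a check of the pilot data and a change of protocol wording. If the check confirms the printed effect sizes, in either order, the target of 30 per group and the analysis stay as they are.

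### Sections 8a, 8b and 8d filter adverse events by perceived relatedness, so the safety count is likely an undercount and should not be read as all-cause incidence (minor)

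*Combined protocol and SAP*

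**What the plan says.** Section 8 of the protocol describes four ways in which safety information reaches the team, and one limit on what is reviewed.

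- **Hotline (8a):** "Subjects will also be given a 24-hour hotline to report any adverse event that they think is related to the study".
- **Day-after contact (8a):** "Subjects will be contacted the day after their study test participation to make sure that they did not experience unexpected or severe reactions". The reactions meant are those to the supplement and to the optional lumbar puncture. The contact is logged.
- **Standing instruction (8d):** subjects are to get in touch as soon as possible "if they experience any adverse events that they think is related to the study".
- **Visits (8d):** researchers collect data at baseline and at 6, 12 and 18 months. No adverse-event question or form is described. Section 8c gives the route as follows: "Safety information will be collected by telephone calls or emails with the participants".
- **Scope of review (8b):** "Safety and untoward events related to the vitamin supplement and optional lumbar puncture will be reviewed".

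Two other statements in Section 8 assume a wider intake. Section 8a has the data monitoring committee look at the occurrence of adverse events every six months. Section 8g suspends the study when a subject reports an unexpected event and lets it resume if the event is found to be unrelated.

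Section 8a also says that recruitment is complete and that only collected samples remain to be analysed. Section 4 says there is no new recruitment. The answers to 8b, 8c and 8d are each marked NA.

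**The concern.** In both subject-initiated routes, the subject decides whether an event is related before anyone on the study team hears of it. An unexpected or slowly developing effect is one that a subject may well not connect with a vitamin. The stated routes are therefore weakest for the events that a six-monthly review and the Section 8g trigger most need to see.

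Two things are at stake. The committee may take a count of attributed events for a count of all events. A low count may also later be cited in support of the Section 11 statement that the dose causes no side effects, which data filtered in this way cannot support.

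**Working it through.** The plan states no adverse-event rate, safety threshold or safety power, so there is no figure to reproduce. The check compares the passages and then illustrates the possible size with assumed inputs.

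**1. The passages side by side**

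| Place | Who starts the contact | Limited by relatedness? |
|---|---|---|
| 8a hotline | Subject | Yes, in the subject's opinion |
| 8d instruction | Subject | Yes, in the subject's opinion |
| 8a day-after contact | Staff | Partly: reactions to supplement and lumbar puncture |
| 8d visits | Staff | Not stated; no adverse-event question described |
| 8b review | n/a | Yes: related events |
| 8a committee review | n/a | No: occurrence of adverse events |
| 8g suspension | n/a | No: relatedness is decided after the report |

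The last two rows need unfiltered input. The first two rows and 8b do not supply it. The visit row is open, and 8c, which names only telephone and email, does not settle it.

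**2. Reach of the day-after contact**

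Assume one contact for each of the four visits. Eighteen months is 1.5 × 365.25 ≈ 548 days, and 4 / 548 = 0.7%. This counts the days on which contact occurs. The documents do not say whether the caller asks about the period before the visit.

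**3. Size of an undercount (assumed inputs)**

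Let n = 30 subjects per arm (Section 6b), p = the true share of subjects with an event, and r = the chance that a subject attributes the event and reports it. Suppose no other route recovers the rest. The expected number recorded is n × p × r, and the share lost is 1 − r.

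- p = 0.4, true count 30 × 0.4 = 12:
  - r = 0.7 records 8.4
  - r = 0.5 records 6.0
  - r = 0.3 records 3.6
- p = 0.2, true count 30 × 0.2 = 6:
  - r = 0.7 records 4.2
  - r = 0.5 records 3.0
  - r = 0.3 records 1.8

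The loss runs from 30% to 70% over this range of r. With r = 1 nothing is lost.

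**4. What would be needed for a difference between arms (assumed inputs)**

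Keep the true rate equal in two arms of 30, and take the chance of a two-sided Fisher exact p ≤ 0.05 by full enumeration.

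| p | r in arm 1 v arm 2 | Expected reports | Chance of p ≤ 0.05 |
|---|---|---|---|
| 0.4 | 0.5 v 0.5 | 6.0 v 6.0 | 2.2% |
| 0.4 | 0.6 v 0.4 | 7.2 v 4.8 | 6.5% |
| 0.4 | 0.7 v 0.3 | 8.4 v 3.6 | 23% |
| 0.2 | 0.7 v 0.3 | 4.2 v 1.8 | 5.7% |

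Equal attribution lowers both counts and creates no expected difference. Unequal attribution can also hide a true difference: true rates of 40% v 20% (12 v 6 subjects) with r = 0.3 v 0.6 give 30 × 0.4 × 0.3 = 3.6 and 30 × 0.2 × 0.6 = 3.6.

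**The case against.** The strongest objection is timing. Section 8 opens by saying that it is not required, the answers that contain the filter are marked NA, and Section 8a says that only sample analysis remains. If follow-up is over, no instruction to subjects can be changed. This stands, and it is why the point is minor and why the fix has a reporting branch. It does not remove the point, because the counts already gathered still need a correct description.

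A reader might infer that events between visits reach the team only when the subject attributes them to the study. That goes too far. The day-after contact is started by staff and does not wait for the subject to volunteer an attribution. It is, however, brief and framed around reactions to the supplement and the procedure.

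A reader might also infer that no all-cause events are collected at visits. The documents do not say so. The first sentence of 8d carries no filter, and open questioning is neither described nor ruled out. Section 8g likewise implies that some events later judged unrelated are expected to be reported. Both weaken any claim that every route is filtered. Neither removes the explicit condition in 8a and 8d or the limit in 8b.

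**Conclusion.** The point holds as a minor one. Sections 8a, 8b and 8d filter safety information by relatedness, in conflict with the committee's task in 8a and with the order of steps in 8g. The safety count is therefore likely an undercount. Its size is unknown, because the documents give neither event rates nor attribution rates. The 30% to 70% loss shown in the working follows from the assumed range of r and from assuming that no other route recovers the missed events.

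The tempting stronger reading is that the filter will produce a false safety difference between arms. The documents do not support it. Section 7a plans no comparison of adverse events by arm, and nothing says that the committee sees counts by arm. A difference would also require attribution to differ by arm. That is possible: no blinding of subjects or staff is stated, Section 6b labels the control arm both placebo and wait-listed, and Section 6c acknowledges skin itching with the supplement. It is not shown.

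**What to change.** **If any follow-up is still open:**

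- Delete the clause in 8a and 8d that makes reporting depend on the subject's own view of relatedness.
- Remove the relatedness limit in 8b as well. Otherwise the review stays filtered after the other two edits.
- Ask every subject the same open adverse-event question at the scheduled visits, say so in 8c and 8d, and record relatedness afterwards as a separate judgement.

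The cost is three wording edits, one question at visits already planned, and more non-serious events to log.

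**If follow-up has ended, as Section 8a suggests:**

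- Report the safety counts as participant-attributed events and not as all-cause incidence.
- Do not use them to support the Section 11 statement about side effects.

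The cost is a table label and a sentence in the report.

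In either case, state which situation applies, since the NA marks and the live text in 8b to 8d now stand side by side.
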